6.8 Efficacy Analysis

Efficacy analysis will be based in the FAS and PPS populations. Primary analysis will be produced in the FAS population. Primary analysis will be repeated in the PPS population as a sensitivity analysis.

Efficacy analysis will be done for the remission-induction period and the entire administration period.

6.8.1 Primary Efficacy analysis

Primary analysis aims to determine if the treatment effect in CR100 response rate at Week 12 is expected to be higher for patients treated with E6011 than for patients treated with placebo.

The Bayesian posterior distribution of the difference in the CR100 rate at Week 12 between E6011 (p1) and placebo (p2) is obtained as p1-p2 posterior distributions. Non-informative prior (Jeffreys) Beta (1/2, 1/2) distributions described by (Oleksandr Sverdlov, Yevgen Ryeznik, & Sheng Wu, January 1, 2015) will be used to calculate p1 and p2 posterior distributions.

A MCMC algorithm will be performed using the following parameters:

- Number of chains = 3
- Initial values for the algorithm in every chain= 3 starting values simulated by a Beta (0.5, 0.5)
- Number of Burn-in = 100000

- Number of Iterations = 200000

Diagnostic for the MCMC convergence will be checked through the Geweke Diagnostics test, Raftery-Lewis Diagnostics, Gelman-Rubin convergence and the autocorrelation efficiency. In case of any issue due to an autocorrelation or non-convergence of the algorithm, the size of the burn-in, the number of iterations and a possible thinning will be evaluated.

Efficacy of E6011 will be confirmed if there was a 50% or more probability of the difference between both groups being 25% according to the posterior distribution.

Probability of the difference between groups being greater than zero will be also calculated.

Subjects with missing primary endpoint data due to premature discontinuation before 12 weeks after administration, or other reasons are treated as non-responders (NRI) in the modeling of the endpoint.

Primary analysis will be performed in the FAS population, and in the PPS population as a supportive analysis.

Two sensitivity analysis will be performed a Last Observation Carried Forward (LOCF) and an Observed Case (OC) imputation for CDAI at week 12 will be used instead of NRI.

Another supportive analysis will be performed following the same logistic regression model (randomization strata and treatment group as fixed factor) used in the secondary analysis.

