#### 9.3.3 Termination of subject treatment or evaluation

The Principal Investigator or Sub-investigator may terminate the subjects' participation in the clinical trial at any time for safety reasons or reasons related to the conduct of the clinical trial. The subjects themselves may request discontinuation of the IMP administration or participation in the clinical trial at any time without providing explanation.

All subjects who discontinue the clinical trial after the start of the IMP administration are to undergo assessments at discontinuation outlined in the study schedule (Table 4) (see "9.5.5" Subject completion and withdrawal").

Note that if any of the following applies to the subject, he or she is to be discontinued.

- (1) The subject has experienced adverse events which make continuation difficult.
- (2) The subject's pregnancy has been confirmed.
- (3) The subject has been deemed to be ineligible to participate in the clinical trial.
- (4) It has become difficult for the subject to continue to use a concomitant drug/concomitant therapy as instructed.
- (5) The subject requires a surgical operation.
- (6) The subject has been diagnosed with gastrointestinal epithelial dysplasia.
- (7) The subject has been diagnosed with a malignant tumour.
- (8) The subject has less than 70 reduction in the CDAI at Week 24 (rescue period) compared to baseline and Week 12.

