# 9.4.7.1 Prohibited concomitant therapies and concomitant drugs 9.4.7.1.1 Prohibited concomitant therapies and concomitant drugs

The concomitant use of the following drugs/treatments shall be prohibited until the end of the extension period (or discontinuation).

- Biologics (infliximab, adalimumab, certolizumab pegol, vedolizumab, ustekinumab and natalizumab, including biosimilars)
- Adrenocorticosteroid injections, enemas and suppositories
- Cyclosporine, mycophenolate mofetil, tacrolimus (excluding topical use)
- Immunoglobulin preparations, blood products
- Cytoapheresis (GCAP)
- Total parenteral nutrition (TPN), peripheral parenteral nutrition (PPN)
- Faecal microbiota transplant, mesenchymal stem cell, etc.
- Live vaccine
- Vaccine with possible risk of infection such as virus vector vaccine using virus having proliferation capability
- Other IMPs/investigational medical devices

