Attachment 6 shows a detailed list of prohibited concomitant drugs.

# 9.4.7.1.2 Restricted concomitant drugs

The following drugs may be used in combination with the IMP, but the dosage and administration may not be changed until Week 12 (or until discontinuation).

In principle, the dosage and administration may not be changed from Week 12 until the end of the extension period, but dosage reduction, discontinuation, increasing dosage after dosage reduction (up to the dosage used at the start of the IMP administration) or resuming administration after discontinuation is allowed. If the symptoms of subjects taking oral adrenocorticosteroids or receiving oral budesonide improve (CR100 achievement), the dosage is to be reduced in principle, using as reference the steroid dosage reduction schedule set forth in Attachment 9.

- Aminosalicylic acid (5-ASA)
- Salazosulfapyridine
- Antibiotic drugs for the treatment of Crohn's disease
- Oral administration of adrenocorticosteroids (less than 30 mg/day of prednisolone equivalent), oral budesonide (9 mg/day or less)
- Azathioprine (AZP)
- Mercaptopurine (6-MP)
- Methotrexate (MTX)
- Enteral nutrient preparation (1,200 kcal/day or less)

The SARS-CoV-2 vaccine may be used concomitantly, but it should not be administered within 7 days before or after the IMP administration.

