Pregnancy test f	0	0							0	0
C. difficile toxin test	0									
CDAI, PRO2		00		0	0		0		0	0
Haematology test, blood	0	0	0	0	0	0	0	0	0	0
biochemistry test, urinalysis										
Adverse event	←				l	ı	1	ı		 
Serum E6011 concentration g,		0	0	0	0	0	0	0	0	0
Serum anti-E6011 antibodies		0		0	0		0		0	0
Serum total FKN concentration h		0	0	0	0	0	0	0	0	0
Blood CD16 + monocytes, etc. (FCM) h		0	0	0	0				0	0
Blood CD16 + monocyte, etc. genetic markers h		0	0	0	0				0	0
Faecal calprotectin		0		0	0		0		0	0

- a. A written consent of the subject is required prior to undergoing tests and medication washout as part of the requirements to participate in this clinical trial.
- **b.** Endoscopic evaluations are performed by a centralised review.
- The IMP is to be administered after completing all assessments scheduled for that day (excluding serum E6011 concentration immediately after the end of administration).
- d. Height is measured during the screening period (on Visit 1) only.
  e. If abnormal neurological symptoms are found after IMP administration, the patient must be examined by a neurologist and undergo brain MRI (T1-weighted, FLAIR and diffusion-weighted imaging) within two weeks.
- Pregnancy test is conducted only in female subjects of childbearing potential.
- Blood samples are collected before and immediately after (within 10 minutes of) IMP administration between Week 0 and Week 10.

**h.** Test results are to be retained by the testing laboratories and not to be shared with Principal Investigators, Sub-investigators and trial coordinators until code break. Blood CD16+ monocytes, etc. (FCM) is only conducted in Japanese subjects

- i. Randomisation is to be performed at baseline (before the start of IMP administration in Week 0).
- j. As many specified tests and evaluations as possible should be conducted for the assessment at discontinuation.
- **k.** E6011 to be administered after the transition to the rescue period or Extension period.
- I. PML onset is to be investigated over the phone, etc. at six months, one year, one and a half years, and two years after the final IMP dose.
- m. E6011 not to be administered when discontinuing at Week 24 for a lack of CDAI response.
- n. To be conducted during the Week 24 visit or 28 days after discontinuation only when discontinuing at Week 24 for a lack of CDAI response.

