# 9.7.1.6.1 Analysis of primary efficacy endpoint

For Week 12 CR100 response rate, the Bayesian posterior distribution of the difference in the CR100 rate at Week 12 between the E6011 group and the placebo group is to be calculated. If there was a 50% or

Date: 18-Apr-2022 version 11.0 Confidential Page 67 of 80

more probability of the difference between both groups being 25% or more, the efficacy of E6011 is confirmed. Noninformative prior distribution is to be used for both the E6011 group and the placebo group.

Subjects with missing primary endpoint data due to premature discontinuation before 12 weeks after administration or other reasons are treated as non-responders - non-responder imputation (NRI).

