4.5 Efficacy endpoints

4.5.1 Primary Endpoints for Efficacy

- CR100 response rate at Week 12, defined as ratio of patients who had CDAI reductions of at least 100 points from baseline to Week 12. CDAI score will be considered as collected in the eCRF by the investigator.

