6.3 Patient Disposition

This section describes patient disposition for both patient study status and the patient analysis populations.

Screened patients are defined as all patients who originally signed the informed consent.

Randomized patients consist of all screened patients with a treatment group allocated and recorded in the IRT database, regardless of whether the treatment kit was used or not.

For the patient study status, the total number of patients in each of the following categories will be presented in the clinical study report using a flowchart diagram or summary table:

- Screened patients
- Screen failure patients and reason for screen failure
- Randomized patients
- Randomized but not treated patients
- Randomized and treated patients
- Patients who discontinued study treatment by main reason for permanent treatment discontinuation

- Status at last study contact: Information collected will be compiled from the patient status panel and information of lost-to-follow-up status from the end of study (EOS) module of the eCRF which was defined as below.

Reason for study discontinuation will be described:

- Progression of the primary disease
- An adverse event unrelated to progression of the primary disease
- An inclusion criterion has turned out to be not met
- An exclusion criterion has turned out to be met
- The patient used prohibited drug(s) or drug(s) with restricted use
- The subject's pregnancy has been confirmed
- Insufficient therapeutic effect (including less than 70 points decrease in CDAI after Rescue Phase)
- The subject requires a surgical operation
- Withdrawal of consent by the subject
- Lost to follow-up
- Discontinuation of the entire Study by the Sponsor
- Other reason by which the Study Treatment is not appropriate as judged by the Sponsor/Investigator

For all categories of patients (except for the screened and non-randomized categories), percentages will be calculated using the number of randomized patients as the denominator. Reasons for treatment discontinuation will be supplied in tables giving numbers and percentages by treatment group. This summary will be provided by treatment group.

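### The primary analysis assigns non-response only for missing Week 12 data, so an observed CR100 response after added Crohn's-directed therapy is counted as a response

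*SAP*

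**What the plan says.** **Endpoint.** SAP 4.5.1 gives the CR100 rate as "defined as ratio of patients who had CDAI reductions of at least 100 points from baseline to Week 12". It sets no condition on concomitant therapy.

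**Non-response.** SAP 6.8.1 states: "Subjects with missing primary endpoint data due to premature discontinuation before 12 weeks after administration, or other reasons are treated as non-responders (NRI". Protocol 9.7.1.6.1 has the same trigger: "Subjects with missing primary endpoint data due to premature discontinuation before 12 weeks after administration or other reasons are treated as non-responders". The synopsis and the secondary-endpoint sections (protocol 9.7.1.6.2, SAP 6.8.2) also act on missing data only.

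**Background therapy.** Protocol 9.4.7.1.1 opens its list, which includes biologics, steroid injections and cytoapheresis, with "The concomitant use of the following drugs/treatments shall be prohibited until the end of the extension period (or discontinuation". Section 9.4.7.1.2, covering oral steroids, immunomodulators and others, says: "The following drugs may be used in combination with the IMP, but the dosage and administration may not be changed until Week 12". Neither section mentions response status.

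**Discontinuation.** Item 4 of the mandatory list in protocol 9.3.3 reads: "It has become difficult for the subject to continue to use a concomitant drug/concomitant therapy as instructed". SAP 6.3 lists this reason for study discontinuation: "The patient used prohibited drug(s) or drug(s) with restricted use".

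**Other analyses.** SAP 6.8.1 adds a per-protocol analysis as supportive, and last-observation-carried-forward (LOCF) and observed-case (OC) analyses as sensitivity analyses. Under SAP 5.1 the per-protocol set excludes major or critical violators. SAP 6.3 leaves the definition of deviations to a separate document.

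**The concern.** The trial asks whether E6011 raises the CR100 rate over placebo by 25 points or more while background treatment is held constant. If a patient's CDAI falls after a new biologic or a higher steroid dose, the stated rule credits that fall to the assigned arm. On placebo this narrows the difference and can hide a real effect. On E6011 it widens the difference and can produce a false confirmation.

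Only 25 patients were enrolled (protocol 9.7.2), so one such patient can decide the result. If the rule is not written before unblinding, any such case has to be classified with the allocation known.

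**Working it through.** **Step 1. Follow such a patient through the plan.**

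- *Leaves early with no Week 12 CDAI:* missing, so a non-responder. The plan covers this case.
- *Stays to Week 12 with a recorded deviation:* the value is observed and imputation does not apply. A fall of at least 100 points is a response.
- *Leaves late:* the discontinuation visit includes CDAI (protocol Table 4), with the instruction "As many specified tests and evaluations as possible should be conducted for the assessment at discontinuation". The Week 12 window in SAP 6.6 is Days 78 to 91, so a discontinuation value on those days could serve as the Week 12 value. The SAP does not say whether discontinuation visits are mapped this way, so this route is possible but narrow.
- *LOCF and OC:* both change only the handling of missing values, and both can use a CDAI taken after the added therapy.
- *Per-protocol set:* it may drop the patient, but dropping is not the same as counting a failure, and the analysis is supportive.

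**Step 2. Reproduce the plan's own figure.** The inputs are the decision rule in protocol 9.7.1.6.1, the Beta(½, ½) priors in SAP 6.8.1 and 20 patients per arm. With x₁ of n₁ E6011 responders and x₂ of n₂ placebo responders, pᵢ ~ Beta(xᵢ + ½, nᵢ − xᵢ + ½), and efficacy is confirmed if P(p₁ − p₂ ≥ 0.25) ≥ 0.50. Summing binomial probabilities over all confirming outcomes at a 40-point true difference gives 80.7% to 83.2% for placebo rates of 10% to 50% (81.3% at 60% v 20%). The stated figure of above 80% reproduces.

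**Step 3. Find the boundary with 25 patients.** The split is not given, so I assume 13 v 12. The minimum number of E6011 responders needed, for 0 to 6 placebo responders, is 4, 5, 6, 7, 8, 9, 10. Two examples:

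- 6/13 v 2/12 gives 0.56 (confirmed); 5/13 v 2/12 gives 0.39 (not confirmed).
- 7/13 v 4/12 gives 0.38 (not confirmed); 7/13 v 3/12 gives 0.55 (confirmed).

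**Step 4. Calculate how often one patient matters.** True rates are assumed.

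- Success lost = Σ Bin(x₁; n₁, p₁) · Bin(x₂; n₂, p₂) over outcomes where (x₁, x₂) confirms and (x₁ − 1, x₂) does not.
- Success gained = the same sum over outcomes where (x₁, x₂) does not confirm and (x₁, x₂ − 1) does.

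| True rates | Lost, 13 v 12 | Gained, 13 v 12 | Lost, 12 v 13 | Gained, 12 v 13 |
|---|---|---|---|---|
| 55% v 15% | 14.5% | 9.7% | 17.7% | 9.0% |
| 50% v 20% | 17.3% | 15.0% | 19.6% | 12.5% |
| 45% v 20% | 17.1% | 16.6% | 18.7% | 13.5% |
| 40% v 20% | 15.5% | 16.9% | 16.2% | 13.4% |
| 50% v 30% | 15.1% | 16.4% | 16.5% | 13.6% |

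**Step 5. Illustrate a systematic effect.** Suppose a further 10% of an arm is counted as responding after added therapy. This share is an assumption; the split is 13 v 12.

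- 60% v 20%, extra on placebo only: the chance of confirming falls from 80.3% to 62.1%.
- 20% v 20%, extra on E6011 only: false confirmation rises from 4.8% to 17.5%.
- 20% v 20%, extra in both arms: it rises from 4.8% to 8.0%.

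**The case against.** The strongest reply has three parts.

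- **Cover through withdrawal.** A detected breach may well end in withdrawal under protocol 9.3.3 item 4 or for the reason listed in SAP 6.3, then no Week 12 value, then imputed non-response. This is true for many cases. But the SAP entry is a disposition category, not an instruction to withdraw, and 9.3.3 does not name use of a prohibited drug or a dose increase.
- **Legitimate alternative.** Using observed values whatever therapy was added is a recognised strategy, and SAP 6.1 calls the analysis exploratory. That stands as far as it goes, but the plan nowhere says that it chose this strategy. A composite rule also fits better with its existing choice to count dropouts as non-responders.
- **Existing reporting.** Deviations are tabulated by arm, and the primary analysis is repeated in the per-protocol set. This would show a problem but would not settle the primary result.

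A reader might also infer more than the documents support:

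- *Every patient who breaches the rules counts as a responder.* Only one with a CDAI in the Week 12 window and a fall of at least 100 points does.
- *The synopsis already calls these patients treatment failures.* It uses that term only for missing endpoint data.
- *Therapy is restricted because it lowers CDAI.* The restriction sections do not give that reason, and the prohibited list includes vaccines and blood products.

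**Conclusion.** The gap is real. Missing data is the only trigger for non-response in the primary analysis, and a response observed after added Crohn's-directed therapy is credited to the assigned arm. Existing provisions cover part of this, not all.

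The size of the effect on this trial cannot be stated, because the documents give no frequency of such cases. The 15-17% and 10-17% (16-20% and 9-14% at 12 v 13) are the chances that the result lies one responder from the boundary, given that one responder in that arm is there to be reclassified. They show how fragile a 25-patient decision is; they do not estimate bias. They rest on the assumed arm split and true rates.

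One might expect added therapy mainly on placebo, and so a bias against E6011, but nothing in the documents fixes the direction. The change should be made, but the finding does not by itself invalidate the design.

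**What to change.** In SAP 6.8.1 and 6.8.2, and in protocol 9.7.1.6, add a rule of this kind:

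> Subjects who, before the Week 12 CDAI, started a therapy listed in protocol 9.4.7.1.1 that was given for, or is able to treat, Crohn's disease, or who for Crohn's disease started a therapy listed in 9.4.7.1.2 or increased it above the Week 0 dose, are non-responders regardless of the observed CDAI.

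- **Limits.** Exclude vaccines, blood products and similar items. Applying the rule to everything in 9.4.7.1.1 would turn a true responder into a failure for reasons unrelated to Crohn's disease.
- **Identification.** Review drug and non-drug therapy records blind before the remission-induction lock. Use the protocol lists: SAP 6.7 omits cytoapheresis, parenteral nutrition, faecal transplant, stem cells and the restricted drugs.
- **Sensitivity.** In LOCF, carry forward only values from before the added therapy. Keep the present observed-value rule as a sensitivity analysis.
- **Consistency.** Protocol 9.3.3 and SAP 6.3 differ on prohibited or restricted drug use as a reason for discontinuation and must be reconciled. The proposed rule concerns analysis only and changes no treatment or stopping rule.

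The cost is a few lines of text and one blinded review. Protocol 9.4.7 already has concomitant drugs and therapies recorded, with some exemptions that the review should check. Response rates may be slightly lower. The documents do not show whether the database has been locked; if it has, the analysis should be reported as post hoc.

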6.8.2 Secondary Efficacy analysis

- a. CDAI response rate (CR70) and remission rate at week 12 will be analyzed using logistic regression model considering randomization strata (Japanese/Non-Japanese and Male/Female) and treatment group as fixed factor. This model will estimate the Odds Ratio between the treatment arms.

Also, the CDAI response rate (CR70, CR100) and remission rate are also to be described by treatment group week 2, week 4, week 8 and week 12.

And finally, CDAI, change and percentage change from baseline will be descriptively analyzed too by treatment group at baseline, week 2, week 4, week 8 and week 12.

- b. PRO2 response rate (PRO2-CR5, PRO2-CR8) and remission rate at week 12 will be analyzed using logistic regression model considering randomization strata (Japanese/Non-Japanese and Male/Female) and treatment group as fixed factor. This model will estimate the Odds Ratio between the treatment arms.

Also, the PRO2 response rate (PRO2-CR5, PRO2-CR8) and remission rate are also to be described by treatment group week 2, week 4, week 8 and week 12.

And finally, PRO2, change and percentage change from baseline will be descriptively analyzed too by treatment group at baseline, week 2, week 4, week 8 and week 12.

- c. SES-CD endoscopic response rate and endoscopic remission rate at week 12 will be analyzed using logistic regression model considering randomization strata (Japanese/Non-Japanese and Male/Female) and treatment group as fixed factor.
Also, the SES-CD endoscopic response rate and remission rate are also to be described by treatment group week 2, week 4, week 8 and week 12.
And finally, SES-CD endoscopic, change and percentage change from baseline will be descriptively analyzed too by treatment group at baseline, week 2, week 4, week 8 and week 12.
- d. Steroid-free CDAI response rate (CR70, CR100) and remission rate will be described by treatment group at week 2, week 4, week 8 and week 12.
- e. Steroid-free PRO2 response rate (PRO2-CR5, PRO2-CR8) and remission rate will be described by treatment group at week 2, week 4, week 8 and week 12.
- f. The dose of adrenocorticosteroids related to Crohn's disease will be described using the change and percentage change from baseline by treatment group at baseline, week 2, week 4, week 8 and week 12.

The dose at baseline is calculated as the sum of doses in mg/day of all adrenocorticosteroids that are taken the baseline day. Doses at every visit are calculated as the sum of all adrenocorticosteroids taken from previous time point to the current visit date, for example, dose at week 2 is the sum of all doses taken from baseline to week 2 date.

Adrenocorticosteroids related to Crohn's disease will be identified as any concomitant corticosteroid at remission induction period in the database that has reported in the eCRF an indication to primary disease (Crohn's disease). Steroid free patients will be identified as patients that are taking any adrenocorticosteroid related to Crohn's disease at baseline and they stop taking them before week 12.

Subjects with missing secondary endpoint data due to premature discontinuation before 12 weeks after administration, or other reasons are treated as non-responders (NRI) in the modeling of the endpoints.

Secondary analysis will be performed in the FAS population and in the PPS population.

